6.7.3 Statistical Modeling: Analysis of Covariance (ANCOVA)

Where appropriate, supportive analyses of clinical efficacy parameters may be completed with Analysis of Covariance (ANCOVA) (Kutner 2005). ANCOVA combines features of both analysis of variance (ANOVA) and regression. It augments the ANOVA model with one or more additional quantitative covariates, which are related to the response variable. The covariates are included to reduce the variance in the error terms and provide more precise measurement of the treatment effects. ANCOVA is used to test the main and interaction effects of the factors, while controlling for the effects of the covariate. In the analyses of this study, ANCOVA will be used for the variables that were measured at the baselines identified in [Figure 1](#). ANCOVA may be implemented to assess treatment group differences in comparisons identified in [Table 8](#) while controlling for the screening measure of the clinical efficacy variable being analyzed. ANCOVA may be utilized where repeated measures are not anticipated for a planned, supplemental analysis or in cases where further understanding of study results will benefit from the use of ANCOVA.

6.7.4 Statistical Modeling: Graphic Displays of Study Results

Graphical displays of study endpoints will be completed and include both observed study data and modeled analyses. Arithmetic means, Least Square Means (LS Means), LS means differences, and appropriate measure of dispersion (e.g. standard deviation, standard error) or confidence intervals may be display in figures to augment the modeled analysis. In general,

graphical displays will be accompany each planned analysis to present study results, utilizing companion numbering aligned with tabular numbering.

Scatter points over the observation time intervals for UX001-CL201 through the 6-month (24 week) time point for UX001-CL202 will be completed for each study endpoint, by treatment pathway (Table 3), to examine trends in results over time of treatments for subjects who roll-over from UX001-CL201. Treatment Naïve subjects enrolled in Part II of UX001-CL202 will have the scatter plots scaled for their participation with treatment 12g/day SA-ER/SA-IR. In general the scatterplots will include, for any given endpoint, all observations for every subject presented in a single figure, color coded for treatment pathways.

Bar charts will be completed for each endpoint where change from baseline is examined and treatment differences are evaluated. Either the mean change or LS Mean's differences, whichever is appropriate for the endpoint, will be displayed to support the statistical analyses performed.

Exploratory scatter plots, and correlations, will be completed to examine study endpoint means (or LS means) compared to Free Sialic Acid (SA), and other serum biomarkers of interest, to explore the treatment effects with the 12g/day SA-ER/SA-IR dose compared to previous doses subjects (Table 3).

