5.1 Study Drug Dosing

Study Drug Dosing for the UX001-CL201 feeder study and for this study UX001-CL202 are mapped to present all possible treatment combinations that a subject may participate in within these two studies (Table 3).

Table 3 Study Drug Dosing Pathways: UX001-CL201 – UX001-CL202

Path	UX001-CL201		UX001-CL202	
	Weeks 0-24	Weeks 24-48	Part I	Part II
1	6g/day	6g/day	6g/day	12g/day
2	3g/day	3g/day	6g/day	12g/day
3	0g/day	6g/day	6g/day	12g/day
4	0g/day	3g/day	6g/day	12g/day
5	N/A	N/A	N/A	12g/day

The 0/6 and 0/3 treatment groups (pathways 3 and 4) may be combined during weeks 0-24 for UX001-CL201 subjects to form a placebo group for comparisons with pathway 5.

The 0/6 and 6/6 treatment groups (pathways 1 and 3) and 0/3 and 3/3 treatment groups (pathways 2 and 4) may be combined to form 3g and 6g treatment groups for comparison with the 12g/day SA-ER/SA-IR dosing.

A total of 5 separate treatment pathways are identified for evaluation. Subjects enrolled in UX001-CL202 who are members of the TNP will have no treatment pathway from the UX001-CL201 study. Subjects who roll over from UX001-CL201 into Part I of this study will continue on a dose of 6g/day SA-ER. These data will be used primarily for additional safety data. All subjects participating in Part II of this study will receive 12g/day SA-ER/SA-IR. The focus of the safety analyses for the primary objective will be on safety at the 6g/day SA-ER and safety at the 12g/day SA-ER/SA-IR doses.

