A GEE model (see Section 6.7.2) will be completed for the week 24 (6 month) primary analysis will include the visits from in Part II of UX001-CL202 (Months 1 to 6) accounting for time on the 12g/day SA-ER/SA-IR treatment with subjects who cross-over from treatment administered in UX001-CL201 (Table 3). The GEE model will incorporate the treatment groups defined in the planned comparisons (Table 8) for HHD % predicted normal strength scores.

Additional Analyses: HHD UE, LE Scores

In addition to the above analyses, additional analyses will be conducted to help further assess both the degree of change over the time course of treatment in both UX001-CL201 and in UX001-CL202 and the effect of crossover from the dosing pathways (Table 3). For each of the treatment pathway groups (or combinations thereof) the HHD UE and LE composite change over time will be evaluated to seek understanding on the various dosing pathways and the effect of the 12g/day SA-ER/SA-IR dosing.

The cross-over treatment pathway groups may be compared with the change observed in prior treatment period HHD UE and LE scores. Trends in the change observed in each parameter will be displayed using graphical techniques. These latter analyses will help evaluate an effect of SA over an extended period of time from UX001-CL201 through UX001-CL202, as well as on the reversal of HHD change for subjects that may have declined during the placebo period (Weeks 0-24 in UX001-CL201). These analyses will help to understand the long term impact of treatment over dosing pathways and assess whether the rate of change in individual subjects has changed significantly from before to after the various treatments received.

Additional Analyses: Serum SA Levels and HHD UE, LE Scores

An analysis of change in mean serum SA level impact on HHD UE, LE scores will be performed. Changes in mean serum SA level observed during the cross-over treatment pathway groups may be compared with the change observed in prior treatment period HHD UE and LE scores. Trends in these changes in observed SA levels and HHD UE and LE scores will be displayed using graphical techniques.

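### The exploratory correlations of endpoint means with free sialic acid in SAP 6.7.4 are confounded with time; show the means as description only, and estimate any association at subject level with visit in the model.

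*SAP*

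**What the plan says.** SAP 6.7.4 commits to the analysis: "Exploratory scatter plots, and correlations, will be completed to examine study endpoint means (or LS means) compared to Free Sialic Acid (SA". Its purpose is "to explore the treatment effects with the 12g/day SA-ER/SA-IR dose compared to previous doses subjects (Table 3", so it spans the dosing periods of both studies. The endpoint plots in the same section cover "Scatter points over the observation time intervals for UX001-CL201 through the 6-month (24 week) time point for UX001-CL202". The section does not say which means are used (by pathway, by visit or by dose), which coefficient, or how time and repeated measures on the same subjects are handled. It labels the work exploratory.

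SAP Table 3 (section 5.1) gives the rollover pathways over UX001-CL201 Weeks 0-24, Weeks 24-48, Part I and Part II. The first three read "1 6g/day 6g/day 6g/day 12g/day", "2 3g/day 3g/day 6g/day 12g/day" and "3 0g/day 6g/day 6g/day 12g/day"; the fourth is 0, 3, 6 and 12 g/day. The text adds: "All subjects participating in Part II of this study will receive 12g/day SA-ER/SA-IR".

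Elsewhere the SAP does allow for time: the models for six-minute walk, gait speed, arm lift and functional scale (6.7.7, 6.7.9, 6.7.11, 6.7.12) have study time points as categorical predictors. SAP 6.5 treats any two-sided p≤0.05 as significant, without multiplicity adjustment.

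**The concern.** In every rollover pathway the later visits are the higher-dose visits, so mean SA and elapsed time move together. A correlation of means with no visit term cannot tell a relation with SA from a drift in the endpoint. GNE myopathy is progressive, and strength and walking tests depend on effort, so drift in either direction is plausible. Decline would make higher SA look harmful; practice gain, or selection of completers, would make it look helpful. Several means also come from the same subjects, so they are not independent points.

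At stake is how the output would be read. Protocol 7.4.3 lists a relation between SA level and dynamometry response among its reasons for the 12 g/day dose, so another SA correlation could easily be taken as evidence for or against it.

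**Working it through.** The documents give no error rate for this correlation, so there is no figure to reproduce.

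**Step 1: dose against time.** Inputs: doses from SAP Table 3. Assumed: Week 0 untreated; visits at weeks 0, 24, 48, 60 (end of Part I), 72 and 84 (Months 3 and 6 of Part II); each visit carries the dose of the period before it. The footnote to SAP Figure 1 says that time in Part I varied, so week 60 is nominal. With r = Σ(d−d̄)(t−t̄) / √[Σ(d−d̄)² Σ(t−t̄)²], t̄ = 48 and Σ(t−t̄)² = 4896:

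| Pathway | Dose at the six visits | Calculation | r |
|---|---|---|---|
| 1 | 0, 6, 6, 6, 12, 12 | 648/√(102×4896) | 0.917 |
| 2 | 0, 3, 3, 6, 12, 12 | 720/√(126×4896) | 0.917 |
| 3 | 0, 0, 6, 6, 12, 12 | 792/√(144×4896) | 0.943 |
| 4 | 0, 0, 3, 6, 12, 12 | 792/√(151.5×4896) | 0.920 |

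Over all 24 pathway-by-visit cells r = 0.916. Adjusting for week inflates variance by 1/(1−0.916²) ≈ 6.2.

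**Step 2: false positives with no SA effect.** Both simulations use 46 rollover subjects (SAP 6.1), SA proportional to dose plus noise, and a Pearson test at p≤0.05. Trend, noise and pathway split are assumptions.

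*Simulation A.* Split 15/15/8/8; no subject-specific slopes; pathway-by-visit mean changes; trend in between-subject SD over the whole 84 weeks. The range is over within-subject correlations of 0.8 to 0.95.

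| Trend over 84 weeks | At correlation 0.9 | Range |
|---|---|---|
| 0 | 2.5% | 2-3% |
| 0.1 SD | 8% | 5-13% |
| 0.2 SD | 27% | 14-48% |
| 0.3 SD | 54% | 31-83% |
| 0.5 SD | 92% | 67-99% |

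On only four dose-level means at correlation 0.9, the rate is 13% at 0.2 SD and 46% at 0.5 SD. With a declining endpoint the average spurious r on the pathway-by-visit means is −0.33 at 0.2 SD; a rising endpoint gives +0.33.

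*Simulation B.* Split 14/14/9/9; subject-specific slopes; 70% of the variance of 24-week change is noise; trend in SD of 24-week change per 24 weeks. Ranges are over repeated runs.

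| Trend per 24 weeks | 24 pathway-visit means | Six pooled visit means |
|---|---|---|
| 0 | 13-16% | 32-33% |
| 0.1 SD | 30-33% | 52-53% |
| 0.2 SD | 64-68% | 83-85% |
| 0.3 SD | 89-90% | 96-97% |

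The trend units differ. Over 84 weeks the trends in B are 3.5 times as large: 0.35, 0.70 and 1.05 SD of 24-week change. If visits 24 weeks apart correlate 0.9, one SD of change is √(2×0.1) = 0.45 between-subject SD, so these are about 0.16, 0.31 and 0.47 between-subject SD over 84 weeks. Most of the apparent gap between the tables is this unit. The rest is largely the subject-specific slopes, which make means of the same subjects drift together even with no average trend.

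**Step 3: with time in the analysis.** In A, a partial correlation adjusted for week rejects in 3-4% of trials at every trend, and the Week 24 data alone in 4-6%. In B, a regression with subject and visit terms and cluster-robust standard errors rejects in 4-6%.

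**Step 4: what is left to estimate.** With the 14/14/9/9 split, the within-subject sum of squares of dose is 5851.5. After removing visit means it is 302.6, and 302.6/5851.5 = 5.2%. All pathways share one dose at Week 0 (0 g), the end of Part I (6 g) and both Part II visits (12 g). They differ only at Weeks 24 and 48, so what remains comes from UX001-CL201, chiefly Week 24.

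**The case against.** The strongest reply is that this is a labelled exploratory display. SAP 6.7.4 names no coefficient or test. The list of planned tables in SAP 8.1 has none relating SA to an endpoint, and the study is not powered for significance. Protocol 7.2 already concedes that progression and treatment effect are hard to separate without a control. No decision is shown to depend on this output: the SA-dynamometry relation in protocol 7.4.3 is tied to the Week 24 data of UX001-CL201, and the later dose changes rest on other reviews. All of this stands and limits the weight of the point. It does not remove it, because the SAP says that the correlations will be done, and 6.5 supplies a significance rule for any p-value attached to them.

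A reader might infer that any time trend produces a significant correlation. That is not supported: at 0.1 between-subject SD over 84 weeks the rate is 5-13%, and the documents give no rate of progression in SD units. A reader might also infer that dose rises at every step. It does not: pathways 1 to 3 have flat stretches, and protocol Part III later lowers the dose for many rollover subjects, outside the SAP's period. Nor are the data empty, since Weeks 0-24 of UX001-CL201 give a randomised comparison of 0, 3 and 6 g/day at the same time point.

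The sharpest objection is to the remedy: visit terms absorb the step to 12 g that all rollovers share, so a visit-adjusted model cannot answer the question in 6.7.4. That is correct (Step 4) and shapes the fix.

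**Conclusion.** The point holds in a limited form. Followed as written, SAP 6.7.4 yields a correlation confounded with time, and a modest trend can often give p≤0.05 with no SA effect. That dose never falls comes directly from SAP Table 3; the correlation of about 0.92-0.94 also needs the nominal visit weeks. The false-positive rates are illustrative: they rest on assumed trend, noise, SA variability and pathway split, and on which means are correlated, none of which the SAP gives.

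A reader might conclude that a better model would recover the effect of 12 g against earlier doses. The design does not allow it: after subject and visit terms only about 5% of the within-subject dose variation remains, and it comes from UX001-CL201. This is a cheap improvement to an exploratory analysis, not a threat to the main comparisons.

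The subject-level split at 0.1 mg/dl in SAP 6.7.6 is a separate matter and is not covered here.

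**What to change.** In SAP 6.7.4:

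- Keep the plots of endpoint means against free SA as description only, by pathway and visit, without r, p or a significance claim.
- If an association between SA and an endpoint is reported, estimate it at subject level with categorical visit in the model and robust standard errors, and label it exploratory.
- State beside it that the estimate is imprecise, that it rests almost entirely on the concurrent dose differences in UX001-CL201 (chiefly the randomised Weeks 0-24), and that it cannot establish an effect of 12 g/day against prior doses.

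The cost is a few sentences of SAP text and minor programming; free SA and the endpoints are already collected per subject. The price is precision: the adjusted estimate will be much less precise than the unadjusted correlation appears.

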6.7.5 Efficacy Analysis: Muscle Strength - Hand Held Dynamometry (HHD)

The hand held dynamometry (HHD) assessment is completed in UX001-CL202 at the Part II time points of Screening/Baseline (last visit in Part I), months 3, 6, 12, 18, 24, 30, 36, and the termination visit (Table 2). The HHD parameters will be summarized into composite scores and GEE analyses will be performed.

HHD Upper Extremity (UE) Composite Score

HHD UE composite scores will be used to evaluate change in upper extremity muscle strength. HHD UE composite scores achieved for the 12g/day SA-ER/SA-IR dosing group at each study time point will be evaluated using descriptive statistics.

A GEE model (see Section 6.7.2) will be completed for the week 24 (6 month) analysis and will include the visits from Part II of UX001-CL202 (Months 1 to 6) accounting for time on the 12g/day SA-ER/SA-IR treatment with subjects who cross-over from treatment administered in UX001-CL201 (Table 3). The primary model will incorporate the treatment groups defined in the planned comparisons (Table 8).

HHD Lower Extremity (LE) Composite Score

HHD LE composite scores will be used to evaluate change in lower extremity muscle strength. HHD LE composite scores achieved for the 12g/day SA-ER/SA-IR dosing group at each study time point will be evaluated using descriptive statistics. The same modelling strategy applied for the HHD UE will be applied for the HHD LE Composite score.

6.7.6 Exploratory Efficacy Analysis: Hand Held Dynamometry (HHD)

HHD Individual Raw Strength Scores

Strength in the individual muscle groups tested by HHD will be assessed using raw scores (as measured in kg) from the right and left sides. Individual muscle groups to be assessed in the upper extremities include pinch (key, tip and palmar), gross grip, shoulder abductors, elbow flexors and elbow extensors. Individual muscle groups to be assessed in the lower extremities include hip abductors, hip adductors, hip flexors, hip extensors, knee flexors and knee extensors.

Raw strength scores achieved for the 12g/day SA-ER/SA-IR treatment group in UX001-CL202 at the Part II time points of Screening/Baseline (last visit in Part I), months 3, 6, 12, 18, 24, 30, 36, and the termination visit (Table 2) will be evaluated for the average of the right and left sides of the individual muscle groups using descriptive statistics. If one side is missing, it will be imputed using the other side.

A GEE model (see Section 6.7.2) will be completed for the week 24 (6 month) primary analysis and will include the visits from Part II of UX001-CL202 (Months 1 to 6) accounting for time on the 12g/day SA-ER/SA-IR treatment with subjects who cross-over from treatment administered in UX001-CL201 (Table 3). The GEE model will incorporate the treatment groups defined in the planned comparisons (Table 8) for raw strength scores.

HHD % Predicted Normal Strength Scores

Strength in the individual muscle groups tested by HHD will be assessed using % of predicted normal scores for the right and left sides. Predicted normal values will be calculated as described in Section 6.5.2. Individual muscle groups to be assessed in the upper extremities include pinch (key, tip and palmar), gross grip, shoulder abductors, elbow flexors and elbow extensors. Individual muscle groups to be assessed in the lower extremities include hip abductors, hip adductors, hip flexors, hip extensors, knee flexors and knee extensors.

Percent of predicted normal scores achieved for the 12g/day SA-ER/SA-IR treatment group in UX001-CL202 at the Part II time points of Screening/Baseline (last visit in Part I), months 3, 6, 12, 18, 24, 30, 36, and the termination visit (Table 2) will be evaluated for the average of the right and left sides of the individual muscle groups using descriptive statistics.

A GEE model (see Section 6.7.2) will be completed for the week 24 (6 month) primary analysis will include the visits from in Part II of UX001-CL202 (Months 1 to 6) accounting for time on the 12g/day SA-ER/SA-IR treatment with subjects who cross-over from treatment administered in UX001-CL201 (Table 3). The GEE model will incorporate the treatment groups defined in the planned comparisons (Table 8) for HHD % predicted normal strength scores.

Additional Analyses: HHD UE, LE Scores

In addition to the above analyses, additional analyses will be conducted to help further assess both the degree of change over the time course of treatment in both UX001-CL201 and in UX001-CL202 and the effect of crossover from the dosing pathways (Table 3). For each of the treatment pathway groups (or combinations thereof) the HHD UE and LE composite change over time will be evaluated to seek understanding on the various dosing pathways and the effect of the 12g/day SA-ER/SA-IR dosing.

The cross-over treatment pathway groups may be compared with the change observed in prior treatment period HHD UE and LE scores. Trends in the change observed in each parameter will be displayed using graphical techniques. These latter analyses will help evaluate an effect of SA over an extended period of time from UX001-CL201 through UX001-CL202, as well as on the reversal of HHD change for subjects that may have declined during the placebo period (Weeks 0-24 in UX001-CL201). These analyses will help to understand the long term impact of treatment over dosing pathways and assess whether the rate of change in individual subjects has changed significantly from before to after the various treatments received.

Additional Analyses: Serum SA Levels and HHD UE, LE Scores

An analysis of change in mean serum SA level impact on HHD UE, LE scores will be performed. Changes in mean serum SA level observed during the cross-over treatment pathway groups may be compared with the change observed in prior treatment period HHD UE and LE scores. Trends in these changes in observed SA levels and HHD UE and LE scores will be displayed using graphical techniques.

Subjects achieving a mean change in serum SA of 0.1 mg/dl or greater over their individual baseline over all visits may be compared to those subjects with <0.1 mg/dl mean change in SA level. Subjects will be placed into either the 0.1 mg/dl or greater mean difference group or the less than 0.1 mg/dl mean difference group, and then the change in HHD UE and LE scores will be compared across these two groups using a GEE model.

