Part II - SA-ER/SA-IR Treatment Period: Successful use of SA replacement therapy in humans is believed to depend upon optimized exposure to the compound. Interim results from the UX001-CL201 study suggest an increased dose of therapy is warranted. In Part II of this Phase 2 open label extension study, 12g SA will be administered orally via 1.5g of

SA-ER tablets and 1.5g SA-IR capsules, QID. The SA-ER/SA-IR dose and regimen for Study UX001-CL202 was selected based on the following additional information:

- **Dose effect at 6g only.** Interim results from UX001-CL201 suggest the 6g SA-ER dose level appears to be at the lower end of the effective range since a clinical efficacy signal was observed but 3g SA-ER had almost no effect.
- **The SA level correlates with treatment effect based on HHD.** The Week 24 interim data imply a positive PD signal and acceptable safety profile suggesting the potential to optimize the therapeutic index by increasing SA exposure.
- **Canine studies show that immediate release most effective way to increase SA.** Studies in normal canines showed that more than proportional increases in absorption of SA are possible if an immediate release formulation was mixed with an extended release formulation. The concept is that the immediate release product enhances stomach absorption which is not well utilized by extended release formulated tablets.
- **QID therapy should support higher SA levels.** Since SA-IR is rapidly cleared, a QID dosing regimen is predicted to provide optimized continuous exposure to SA. Administration of a 12g total daily dose of SA would therefore be divided into 4 equal doses of 3g each (1.5g SA-ER + 1.5g SA-IR), representing only a 50% increase for each dose.
- **Safety of very high SA doses.** In a chronic toxicology study in rats, the NOAEL was 2000 mg/kg SA, which provides a safety margin of approximately 1.4-fold for the proposed 12g/day dose level. In a 6 month oral toxicity study in dogs, the NOAEL was 2000 mg/kg SA, which provides a safety margin of approximately 5-fold for the human 12g/day dose level.
- **Single doses of 6g SA-ER given in one dose were well tolerated.** In the Phase 1 PK and tolerability study, 6g SA-ER was administered to GNE Myopathy subjects in a single oral dose and was well tolerated with no SAEs observed.

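### SAP 6.7.6 pairs the serum SA change of the cross-over period with the strength change of the period before it, so this optional comparison cannot show an impact of SA on strength

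*SAP*

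**What the plan says.** SAP 6.7.6, under its additional analyses of serum SA levels and HHD scores, opens with a commitment: "An analysis of change in mean serum SA level impact on HHD UE, LE scores will be performed". The next sentence says what is set against what: "Changes in mean serum SA level observed during the cross-over treatment pathway groups may be compared with the change observed in prior treatment period". The strength side, in full, is that these SA changes "may be compared with the change observed in prior treatment period HHD UE and LE scores". A display sentence comes after it: "Trends in these changes in observed SA levels and HHD UE and LE scores will be displayed using graphical techniques".

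The subsection just before, on HHD scores alone, contains a near-identical sentence: "The cross-over treatment pathway groups may be compared with the change observed in prior treatment period HHD UE and LE scores". Its purpose there is to see whether a subject's rate of strength change differs before and after a change of treatment.

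The SAP relates SA to strength in two other places:

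- Later in 6.7.6, an optional grouped comparison begins "Subjects achieving a mean change in serum SA of 0.1 mg/dl or greater over their individual baseline over all visits may be compared" with the remaining subjects. HHD change is then compared between the two groups by GEE.
- Section 6.7.4 plans exploratory scatter plots and correlations of endpoint means against free SA.

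In protocol 7.4.3, one of the listed reasons for the Part II dose and regimen is "The SA level correlates with treatment effect based on HHD".

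**The concern.** An analysis of impact needs the exposure to come before the outcome or run alongside it. Here the exposure is the SA change after cross-over and the outcome is the strength change before cross-over. Whatever association appears, it cannot be an effect of that SA change on that strength change.

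Two things are at stake, both modest. A programmer who follows the sentence produces a comparison that does not serve its heading, and may report no SA relationship when one exists. If a subject's SA changes in successive periods are related, the comparison can also show an association that reflects only that link, in either direction. The subject matters because the protocol uses an SA-strength correlation in its dose rationale, and Part II provides new data in which to look at it.

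**Working it through.** The plan states no figure for this analysis, so there is nothing to reproduce. The check is mainly textual.

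**1. Period attached to each side (SAP 6.7.6).**

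| Sentence | Current-period side | Prior-period side | Can it serve its aim? |
|---|---|---|---|
| HHD subsection | HHD in the cross-over pathway groups | HHD change | Yes: before versus after on one measure |
| SA subsection | SA change in the cross-over pathway groups | HHD change | No: outcome precedes exposure |

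The two sentences share their second half. Replacing HHD by SA on one side turns a valid before/after comparison into a mismatched pair.

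**2. Does another SA-strength analysis fix the interval?**

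- The GEE comparison in 6.7.6 has no prior-period restriction. However, it averages SA change over all visits and names neither the baseline nor the HHD window. SAP 6.5.8 lists several candidate baselines. SA measured after an HHD reading can therefore count towards the exposure for that reading.
- The correlations in 6.7.4 name no interval.
- In the planned table list (8.1), the association tables 507 to 513 cover HHD, FAS, 6MWT, gait speed and arm lift. None relates SA to HHD.

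So no place in the SAP ties SA change and HHD change to one interval.

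**3. Can same-interval changes be formed from the planned data?**

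- HHD in Part II (SAP 6.7.5): baseline, Months 3, 6, 12, 18, 24, 30, 36, termination.
- Free serum SA in Part II (SAP 6.9.1): baseline, Months 1, 3, 6, 12, 24, 36, termination.
- Both: baseline, Months 3, 6, 12, 24, 36, termination. Within the 6-month analysis: baseline, Month 3 and Month 6.

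SAP 6.10.2 also lists SA at Months 18 and 30. The smaller set in 6.9.1 is used here, and the conclusion does not depend on which is right. The data support the right comparison; only the wording is wrong.

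**4. Illustration of what the mismatch costs.** The SAP names no test for this comparison and gives no correlation. Assume n = 46 (the approximate number of rollover subjects), a two-sided Pearson test at 0.05, and a true same-period correlation ρ of 0.3, 0.4 or 0.5. Let c be the correlation between a subject's successive SA changes. If prior-period strength depends on later SA change only through prior SA change, the expected prior-period correlation is c × ρ. By the Fisher approximation, power is about Φ(atanh(r) × √(46 − 3) − 1.96), with √43 = 6.557.

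| ρ | Same-period: atanh(ρ) × 6.557 | Power | Prior-period, c = 0 | Prior-period, c = −0.5: r | Share significant |
|---|---|---|---|---|---|
| 0.3 | 0.3095 × 6.557 = 2.030 | 53% | 5% | −0.15 | 17% |
| 0.4 | 0.4236 × 6.557 = 2.778 | 79% | 5% | −0.20 | 26% |
| 0.5 | 0.5493 × 6.557 = 3.602 | 95% | 5% | −0.25 | 39% |

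The last column uses atanh(0.15), atanh(0.20) and atanh(0.25) = 0.1511, 0.2027 and 0.2554. Multiplied by 6.557 these give 0.991, 1.329 and 1.675, and the small opposite tail is included. Simulation of 4,000 trials per setting agrees to within about two percentage points.

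The value c = −0.5 is what arises when two successive changes share a middle SA value and the three values are independent with equal variance. It is an assumption, not a bound. If c is positive, as it could be for subjects whose SA rises at each dose step, the prior-period correlation has the expected sign but still does not measure the effect of the later SA change.

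**The case against.** The strongest case on the other side has four parts.

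- **The comparison is optional and other analyses exist.** This stands. The pairing sentence says the comparison may be made. The GEE and the correlations look at SA and strength without a prior-period restriction. A reader might infer that the plan cannot answer the exposure-response question at all; the documents do not support that.
- **The phrase is template wording.** Near-identical prior-period sentences recur in SAP 6.7.7 to 6.7.12, each time for one endpoint before and after cross-over. The authors may have meant to show SA and HHD together in each period. This explains the sentence but does not correct it, since no other text supplies the intended interval.
- **The displays are not specified.** This stands. A reader might infer that the trend plots will put later SA against earlier strength. The SAP gives no axes or pairing for them, so that cannot be asserted.
- **The detection rates belong to a test the SAP does not name.** This stands. The study is declared not powered for significance testing (SAP 6.1), exposure-response is not among the listed objectives, and nothing in the documents obliges this analysis to confirm the dose rationale. The rates show the direction of the problem and are not properties of the plan.

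**Conclusion.** Wrong as written, low severity. The only stated period pairing for the SA impact analysis puts the outcome before the exposure, so that comparison cannot serve its stated aim. This rests on the literal wording of one sentence and needs no numerical assumption.

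The reach is limited to one optional, exploratory comparison in an unpowered study. The two other SA-strength analyses keep the question open, with the reservation that neither states a common interval and the GEE version can let SA measured later count as exposure.

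The illustrative loss, from roughly 53% to 95% detection down to about 5%, holds only under the assumed correlations, 46 subjects, a Pearson test and unrelated successive SA changes. A wrong-signed result further requires a negative correlation between those changes.

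**What to change.** Replace the pairing sentence in SAP 6.7.6 with: *Change in serum SA will be related to change in HHD UE and LE composite scores over the same interval, with the same start and end visit (Part II baseline to Months 3 and 6).*

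Apply the same baseline and window to the grouped GEE comparison that follows, so that SA measured after an HHD reading does not count as its exposure. If the prior-period HHD pairing is kept for any reason, label it a check that is not evidence of SA effect.

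The cost is one replaced sentence and one added clause. Both measures are already scheduled at Part II baseline, Month 3 and Month 6, so no visit, sample or assessment is added.
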